**March 3, 2017**

## **Study Protocol**

Study titled 'Comparison of the Effectiveness of Proprioceptive Neuromuscular Facilitation Exercises and Shoulder Mobilization Patients with Subacromial Impingement Syndrome: A Randomised Clinical Trial' was approved by Marmara University Faculty of Medicine Clinical Researches Ethics Committee meeting on 03.03.2017 with approval number: 09.2017.200.

The participants in the study were informed about the aim, duration and the programs to be applied throughout the study. Volunteer Information Form has been signed and approved in accordance with the standards deemed appropriate by the Clinical Researches Ethics Committee of Marmara University Faculty of Medicine (This form can be seen on Informed Consent Form (ICF) section). The study was conducted in accordance with the Declaration of Helsinki.

### **Randomization of the Study Groups**

Individuals with Subacromial Impingement Syndrome (SIS) who applied to Sevgi Medical Center for physiotherapy and rehabilitation were invited to participate to the study. Individuals who volunteered to participate and whom met the criteria for participation were randomized with 'Research Randomizer' program and divided into three groups. In all three groups participants received conventional physiotherapy program. The shoulder mobilization techniques was added to the program of the Group II (The Shoulder Mobilization Group). Proprioceptive Neuromuscular Facilitation (PNF) techniques was added to the program of the Group III (The PNF Group).

### **Inclusion Criteria**

- Volunteered to participate,
- Aged between 25-65 years old,
- Having the diagnosis of Subacromial Impingement Syndrome (SIS),
- Having shoulder pain at least for four weeks

## **Exclusion Criteria**

- Patients with a neuromuscular disease, pregnancy, history of cancer, unstable angina, a history of surgery at neck, shoulder, elbow or/and hand, communication problem, pulmonary and/or vascular problems, systemic anti-inflammatory joint disease, any condition which was contraindicated for electrical stimulation and/or exercise, cervical disc herniation or radiculopathy, previous physiotherapy on the same shoulder due to SIS, a history of corticosteroid injection in last three months, any orthopedic, rheumatologic, or congenital condition that effect the targeted shoulder

## **Applied Evaluations**

### **1. Shoulder Pain**

Pain was defined with Visual Analog Scale (VAS). A 10-cm long horizontal visual analog scale (VAS) with marks 0 point (no pain) and 10 point (unbearable pain) was used for evaluating the pain severity. The patients were asked to mark the representing point of their pain levels. The values were recorded in cm. The pain severity was asked in three occasions as: at resting (VASr), during activity (VASa) and during night (VASn).

### **2. Function of the Shoulder**

The Disabilities of the Arm, Shoulder and Hand (DASH) Score was used to evaluate the upper extremity physical function. DASH includes two modules as disability / symptom section and work section. The scores are ranged between 0-100. Higher scores indicate lower functionality.

In addition to DASH, the Constant-Murley score was used to evaluate the functionality of the shoulder. Constant-Murley score is a 100-point scoring system and consisted of four sub-scores as pain (15 points), daily living activities (20 points), active range of motion (40 points), and muscle strength (25 points).

### **3. Range of Motion**

The active range of motion was assessed by using a universal goniometer.

#### **4. Muscle Strength**

The muscle strength of shoulder flexion, shoulder abduction, shoulder adduction, shoulder external rotation, and shoulder internal rotation were determined by using Baseline Push-Pull (New York, USA) dynamometer. The dynamometer was placed in a 90 degrees angle on the location and the patient was asked to contract in maximum for two seconds and then maintain this position for five seconds. Two assessments were performed, and average values were recorded. Pain was avoided during the measurements.

#### **Treatment Program**

The participants in our study were all treated in Sevgi Medical Center five days a week for 4 weeks, a total of 20 sessions (Duration of one session is 60 minutes) and follow-up for 12 weeks, total follow- up time was 16 weeks.

The conventional physiotherapy consisted of electrotherapy and exercise approaches. The electrotherapy program consisted of infrared application (for 15 minutes, from 70 cm distance with Hanau 201, Germany device), conventional TENS was applied in an encircled region (for 20 minutes with Intelect 2778 Combo, Chattanooga Group device; with 4 electrodes, 100 Hz, 100 msec), and therapeutic Ultrasound was applied (for 3 minutes with Intelect 2778 Combo, Chattanooga Group device; 1 MHz, power: 1,5 W/cm^2).

A physiotherapist supervised entire exercise program performed following the electrotherapy program. Elastic resistive exercises were added at the week three. While, the first set of wand exercises and elastic resistive exercises was performed under supervision, two sets were given as the home exercise program.

The PNF group received PNF exercises with contract-relax technique, in the patterns of “flexion-abduction-external rotation”, “extension-adduction-internal rotation”, “flexion-adduction-external rotation” and “extension-abduction-internal rotation” along with the verbal and manual facilitation of the physiotherapist.

In the mobilization group, while the shoulder joint was placed in the traction, anterior, posterior, and inferior glidings and circumduction were applied to the humerus for 2-3 minutes. All mobilization applications were performed in painless ROM limits. The degree of traction and glidings were increased as the relaxing obtained in the tissues.

**Comparison of the Effectiveness of Proprioceptive  
Neuromuscular Facilitation Exercises and Shoulder  
Mobilization Patients with Subacromial Impingement  
Syndrome: A Randomised Clinical Trial**

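### Does the TENS setting of 100 Hz with an unlabelled 100 msec call for a change to the plan?

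*Combined protocol and SAP*

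**What the plan says.** The Treatment Program section describes the conventional programme as electrotherapy followed by supervised exercise: "The conventional physiotherapy consisted of electrotherapy and exercise approaches". Electrotherapy has three parts: infrared for 15 minutes, TENS for 20 minutes and ultrasound for 3 minutes.

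For TENS, the text says that "conventional TENS was applied in an encircled region", gives the application time and device as "for 20 minutes with Intelect 2778 Combo, Chattanooga Group device", and then lists the settings "with 4 electrodes, 100 Hz, 100 msec". The 100 msec carries no label. No other section gives a TENS pulse duration, train length, burst rate or intensity, so nothing elsewhere settles what it means.

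The ultrasound entry, on the same device, reads "with Intelect 2778 Combo, Chattanooga Group device; 1 MHz, power: 1,5 W/cm" per square centimetre.

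The section on randomization states who receives this programme: "In all three groups participants received conventional physiotherapy program". Mobilization is added in Group II and PNF in Group III.

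**The concern.** A reader who meets a frequency followed by a duration will probably take the second figure as the pulse duration. On that reading the two settings exclude each other, because a pulse cannot outlast its own cycle. The other reading, a train of pulses, removes the conflict but leaves the pulse duration and the train repetition rate unstated, and the text mentions no trains. Either way, another centre could not set the device from this line alone.

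What would be at stake is the description of the background treatment. It is the whole treatment of the conventional-only group and the base on which mobilization and PNF are tested. If the setting had differed between groups, or if some result depended on it, an ambiguous entry could matter for interpretation.

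**Working it through.** **Inputs** (Treatment Program): frequency 100 Hz; unlabelled time 100 msec; application time 20 minutes. From the section on randomization: all three groups receive the programme.

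**Cycle length.** 1000 ms / 100 Hz = 10 ms.

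**Reading 1, pulse duration.** 100 ms / 10 ms = 10, so the pulse would fill 1000% of its cycle. Pulses of 100 ms could repeat at no more than 1000/100 = 10 Hz. This conflicts with 100 Hz.

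**Reading 2, interval between pulses.** An interval of 100 ms also implies at most 10 Hz. This conflicts with 100 Hz.

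**Reading 3, train length.** 100 per second × 0.1 s = 10 pulses per train. This is possible, but the pulse duration and train rate are then missing.

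**Is the 20-minute application a second conflict?** Pulses: 100 × 20 × 60 = 120,000. At 0.1 s each: 12,000 s = 200 minutes, and 200/20 = 10. This is the ratio from Reading 1 multiplied through by the session length, and any application time gives the same 10. Nothing contradicts the 20 minutes.

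**Does the setting reach the comparison?** Suppose the outcome for a patient in group g is b + a(g) + error, where b is the contribution of the shared programme at whatever setting was used, and a(g) is what the group's added treatment contributes, with a(I) = 0.

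- Group II minus Group I: (b + a(II)) − (b + a(I)) = a(II).
- Group III minus Group I: a(III).
- Group II minus Group III: a(II) − a(III).

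The term b cancels in each. The SAP compares groups with Kruskal-Wallis and Mann-Whitney U tests, which use ranks. Adding the same b to every patient's value leaves all ranks, and so both test statistics, unchanged. If b does not simply add but modifies the effect of mobilization or PNF, the comparison is still between randomized groups on a common background. The setting then affects how far the result carries to other backgrounds, and it does not bias the comparison.

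**Does any planned quantity use the figure?** The evaluations are VAS pain, DASH, Constant-Murley, range of motion and muscle strength. The SAP gives the software, the 0.05 significance level, a normality test and the two group tests. None takes a TENS setting as input.

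**The case for a change.** The strongest case for acting is that every reading ends in a contradiction or an incomplete setting, and that this follows from the definition of frequency with no outside source. The authors chose to give device, electrodes, frequency and duration, so what they give ought at least to be possible. TENS is not trivial in the programme either: at 20 minutes it is the longest of the three electrotherapy parts and, if electrotherapy falls within the 60-minute session, 20/60 or one third of it. Correcting one line costs almost nothing.

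The arithmetic stands, and so does the observation that the text cannot be used as it is to set the device. Several supporting arguments are weaker.

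- The contradiction depends on a label that the text does not supply. Without that assumption, what the document shows is one unlabelled figure.
- The contrast with ultrasound, where the intensity is labelled, shows little: the 1 MHz in the same bracket is unlabelled, as is the 100 Hz for TENS.
- It does not follow that treatment could not be delivered. The section reports treatment in the past tense on a named device. If the pair is impossible, it was not the setting used, and the fault is in the record.
- Labelling the duration would not by itself make TENS reproducible, since no intensity is given.
- The conflict turns on one unit prefix in text read from a PDF. The text shows no sign of a misread, but the page image is not available here, so a misread cannot be excluded.

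**Conclusion.** The discrepancy is real if 100 msec is a pulse duration: a factor of 10 against the 10 ms cycle. If it is a train length, the entry is incomplete. In either case it is a clerical matter or a missing detail in the record of a treatment common to all groups. Its effect on the between-group comparison, the error rate and the planned tests is nil.

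This rests on two assumptions: that the same TENS setting was used in all three groups, which the section on randomization supports by giving every group the conventional programme, and that no analysis by TENS setting is intended, since the SAP mentions none.

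The frequency and the duration still have to be reconciled against the source page and the device record whenever the treatment is reported, with the duration labelled. That corrects the record and alters nothing in the design or analysis. This review takes no position on which figure or unit is right.

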**Statistical Analysis Plan (SAP)**

**(Pages 6 – 7)**

**March 3, 2017**

## **Statistical Analysis Plan (SAP)**

The statistical program Statistical Package for Social Sciences (SPSS) Version 16.0 (SPSS Inc., Chicago, IL, USA) was used in the data analysis of the study. The p value of  $p<0.05$  was considered to be statistically significant in the data analysis. Shapiro-Wilks test was used to investigate the appropriateness of the variables to normal distribution. Kruskal-Wallis and Mann-Whitney U tests were used to compare the groups.

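### The plan neither records nor analyses adverse events, stopped sessions or harm-related withdrawals in any arm, and the SAP does not count patients who worsened

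*Combined protocol and SAP*

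**What the plan says.** All three groups receive conventional physiotherapy (infrared, TENS, ultrasound and exercise). Mobilization is added in Group II and PNF in Group III (protocol, Randomization of the Study Groups and Treatment Program). Treatment is 20 sessions over four weeks, followed by 12 weeks of follow-up. Part of the exercise is done away from the clinic: "two sets were given as the home exercise program".

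Precautions appear in three places. For mobilization, "All mobilization applications were performed in painless ROM limits". For dynamometer testing, "Pain was avoided during the measurements". At entry, the Exclusion Criteria rule out "any condition which was contraindicated for electrical stimulation and/or exercise".

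The Applied Evaluations are VAS pain (at rest, in activity and at night), DASH, Constant-Murley, active range of motion and muscle strength. On analysis, the SAP names a normality test, a significance level and the statement that "Kruskal-Wallis and Mann-Whitney U tests were used to compare the groups". Neither document, as supplied, mentions adverse events, interrupted sessions, withdrawals or their reasons, or a safety table.

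**The concern.** The trial's purpose is to compare two hands-on techniques added to a common programme. A conclusion that one is better is normally read as a judgement on benefit and harm together. Here the harm side would be empty: if one technique produced more flares or more abandoned sessions, nothing in the planned data would say so.

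There is a second consequence. Sessions stopped for pain reduce the treatment a patient actually receives, and patients who leave because of pain may give no later score. Both affect how the efficacy comparison is read, and neither would be visible. Events that were never recorded cannot be recovered at analysis.

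**Working it through.** The documents give no figure to reproduce: no sample size, event rate or dropout allowance. The check is therefore to take each kind of harm and ask where the plan as written would record it.

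1. **Lasting worsening of pain or function.** It could be recorded. VAS can rise. DASH can rise, and for DASH "Higher scores indicate lower functionality". Constant-Murley (which has its own pain sub-score), range of motion and strength can fall. Seeing a change needs a score before treatment and one after it, and the protocol does not state assessment times. The data may exist, but the SAP does not define or count worsening.
2. **A flare after a session that settles before the next assessment.** No evaluation asks about it, and a later VAS or DASH score need not reflect it.
3. **A skin reaction to electrotherapy.** None of the listed evaluations covers it.
4. **A session shortened or stopped.** The protocol fixes the number and length of sessions but provides no record of departures or their causes.
5. **Withdrawal because of pain or another harm.** No reasons are collected. Such a patient may be missing from later scores, so the scales cannot stand in for the missing reason.
6. **Symptoms during home exercise.** The protocol provides for no question about them.

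On the analysis side, Kruskal-Wallis and Mann-Whitney tests ask whether one group's values tend to rank above another's. They do not report how many patients deteriorated. A patient who worsens contributes a rank, but no count or table is planned.

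Item 1 can therefore be repaired by tabulation if pre-treatment scores exist. Items 2 to 6 cannot, because nothing is collected.

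The opportunity to collect is already there. Five sessions a week × 4 weeks = 20 contacts per patient in every arm. The remaining period is 16 − 4 = 12 weeks, for which no assessment visits are specified.

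**The case against.** The strongest reply is that the outcome scales already move in both directions, so the plan is not blind to harm. This stands in part. A reader might infer that the trial can rank the techniques only on benefit and cannot see who was made worse. The documents do not support that, because item 1 above is observable in principle. The reply does not reach the other items.

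A reader might also infer that the plan itself names pain and contraindications as risks of the two techniques. It does not. One statement describes how mobilization was delivered, one concerns strength testing, and one is an eligibility rule. The case for recording harm does not need that premise.

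A third tempting inference is that the Treatment Program contradicts itself by giving a pain limit for mobilization and none for PNF. Silence about one technique does not conflict with a statement about another, so there is nothing to reconcile.

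It is also fair to say that electrotherapy and home exercise are described as part of the conventional programme given to all arms. Events from them are not, in themselves, evidence of a difference between techniques. That is why recording should cover all three arms alike. Patients also attend five days a week during treatment, so staff could hear of symptoms at home; the plan simply does not provide for writing them down.

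Finally, the consent form was not available. It might describe risks or tell patients how to report events. This limits what can be said about its content, but it does not put a harm outcome or a safety analysis into the evaluations or the SAP.

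**Conclusion.** The point holds in a limited form. In the documents as supplied, no arm has any planned collection or analysis of adverse events, shortened or stopped sessions, or harm-related withdrawals, and the SAP does not count patients who worsened on the scores it does have. The planned efficacy tests remain usable, but a claim that one technique is preferable would rest on efficacy scores without harm data.

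The effect cannot be quantified. Arm size and event rates are not stated, and the division of the 16 weeks into treatment and follow-up measures calendar time, not missed harm. Nothing in the documents shows that the techniques actually differ in harm or that any conclusion would change. The verdict assumes that no separate event record exists outside the supplied text. The recommendation rests on the low cost of the remedy and on the fact that uncollected events cannot be reconstructed later.

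**What to change.** **Collection.** In the record of each of the 20 existing sessions, in all three arms, the treating physiotherapist notes:

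- any provoked pain or flare;
- any skin reaction;
- whether the session was shortened or stopped, and why;
- symptoms with home exercise since the last session.

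Ask the same at whatever follow-up assessments take place. Record the reason for every withdrawal.

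**Analysis.** Add to the SAP one descriptive table by arm giving patients with any event, sessions stopped and harm-related withdrawals. Where pre-treatment scores exist, add the number of patients whose VAS or DASH is worse than before treatment at each later assessment. This last part needs no new measurement.

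If treatment has already been completed, the worsening table can still be built from existing scores. The report should then say plainly that harms were not systematically collected.

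**Cost.** Brief recording at sessions that already take place, and one table. Asking at follow-up adds little wherever an assessment is held, but the protocol would have to say when those are. The harms comparison will be imprecise and should be presented as descriptive.

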**Statistical Analysis Plan (SAP)**

**(Pages 6 – 7)**

**March 3, 2017**

## **Statistical Analysis Plan (SAP)**

The statistical program Statistical Package for Social Sciences (SPSS) Version 16.0 (SPSS Inc., Chicago, IL, USA) was used in the data analysis of the study. The p value of  $p<0.05$  was considered to be statistically significant in the data analysis. Shapiro-Wilks test was used to investigate the appropriateness of the variables to normal distribution. Kruskal-Wallis and Mann-Whitney U tests were used to compare the groups.

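### The SAP applies one p<0.05, with no adjustment described, to at least 11 outcomes in three arms and names no primary outcome, time point or contrast

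*Combined protocol and SAP*

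**What the plan says.** The SAP is a single paragraph. It sets one threshold: a p value below 0.05 "was considered to be statistically significant in the data analysis". On the comparison itself it says only that "Kruskal-Wallis and Mann-Whitney U tests were used to compare the groups". It does not say whether the pairwise tests depend on the overall test, and it exempts no outcome from the threshold.

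The Protocol's Applied Evaluations section lists the outcomes without ranking them:
- Shoulder Pain: three VAS scores (rest, activity, night).
- Function of the Shoulder: DASH and Constant-Murley. It adds that "DASH includes two modules as disability / symptom section and work section".
- Range of Motion: active range, directions not listed.
- Muscle Strength: five directions.

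Under Randomization of the Study Groups, participants were "divided into three groups", and "In all three groups participants received conventional physiotherapy program". Mobilization was added in Group II and PNF in Group III. Treatment Program gives 4 weeks of treatment and 12 weeks of follow-up, but no time point is tied to the group comparison.

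**The concern.** Nothing says which result carries the conclusion. The study title, "Comparison of the Effectiveness of Proprioceptive Neuromuscular Facilitation Exercises and Shoulder Mobilization", points to PNF versus mobilization. The add-on design equally supports comparing either added technique with conventional physiotherapy alone. With at least 11 outcomes and three possible contrasts, any one of many tests falling below 0.05 can be called statistically significant and reported as proof of effectiveness.

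If the three programmes were in truth equivalent, the plan could still produce such a result, and it contains no rule for telling it from a real effect. Patients and therapists could then be told that PNF or mobilization adds benefit on the strength of a chance finding.

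**Working it through.** The documents state no familywise error, power or sample size, so there is no figure of theirs to reproduce.

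**Outcome count.** From Applied Evaluations: 3 (VAS) + 1 (DASH) + 1 (Constant-Murley) + 1 (range of motion) + 5 (strength) = 11. This is a minimum. Analysing both DASH modules makes it 12, and separate range-of-motion directions or Constant-Murley sub-scores would add more.

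**Contrasts.** Three arms give 3 pairwise contrasts, so 11 × 3 = 33 pairwise tests at one time point.

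**Reference case.** With one test per outcome and independent outcomes, the chance of at least one false positive is 1 − 0.95^11 = 1 − 0.569 = 0.431. The outcomes are surely correlated, so this is only a reference.

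**Illustration with correlated outcomes.** All of the following are assumptions: 11 equally correlated normal outcomes, 20 per arm, one time point, identical programmes, two-sided 0.05, and Mann-Whitney tests only after a significant Kruskal-Wallis test. Simulation with 20,000 replicates:

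| Between-outcome correlation | Any false significant result | An add-on arm falsely superior to conventional care or to the other add-on |
|---|---|---|
| 0.3 | 37.5% | 29.5% |
| 0.5 | 31.6% | 24.8% |
| 0.7 | 23.8% | 18.6% |
| 0.8 | 19.4% | 15.1% |
| 0.9 | 14.0% | 10.8% |

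A large-sample calculation of the first results column (100,000 replicates) gives 37.9% at correlation 0.3 and 13.5% at 0.9.

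**Sensitivity of the first results column (correlation 0.3 and 0.9).**
- 10 per arm: 35.6% and 14.0%. 40 per arm: 37.8% and 14.3%.
- 12 outcomes: 39.8% and 14.6%.
- Pairwise tests not conditional on Kruskal-Wallis: 69.5% and 30.7%.
- Two time points, still conditional, between-time correlation assumed 0.6: 56.8% and 24.0%.
- Correlation 0.95 (large sample): 10.6%.

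**Why outcome, time point and contrast all need naming (large sample).**
- Fixing only the contrast, with 11 outcomes at one time point, leaves 37.4% (correlation 0.3) to 13.3% (0.9).
- Fixing the outcome and time point, but testing all three pairs unconditionally, leaves 12.3%.
- Fixing only the outcome, with one Kruskal-Wallis test at each of two time points (between-time correlation assumed 0.7), leaves 8.6%.
- One outcome, one time point and one test gives 5%.

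**The case against.** The strongest reply is that the SAP claims no familywise error rate, so it breaks no promise, and that the percentages come from assumptions rather than from the documents. Both statements are true. The absence of adjustment is also read from silence: the SAP does not say in words that it will not adjust. What remains is that one threshold is stated for the whole analysis, nothing is exempted, and no result is designated to carry the conclusion. That defect stands without any percentage.

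Four stronger or different readings are tempting, and the documents do not support them.
- **The error rate of this trial is 14% to 38%, or as high as 70%.** The documents fix neither correlations, sample size, test order nor time point. The first range is a scenario. The higher figures need unconditional pairwise testing or a second analysed time point, which are not stated either.
- **The low end is the realistic one, because Constant-Murley overlaps the other measures.** Its pain, motion and strength parts make up 15 + 40 + 25 = 80 of 100 points, but the Protocol does not say they are scored from the same VAS, goniometer or dynamometer readings. Even if Constant-Murley is built entirely from the other outcomes, the large-sample rate falls only from 38% to 36% at correlation 0.3, and from 31% to 29% at 0.5. One composite says little about the correlation among the other ten outcomes.
- **The past tense shows that results were chosen after the fact.** The Protocol writes "The study was conducted in accordance with the Declaration of Helsinki", and the SAP is also in the past tense, although both carry a date of March 3, 2017. This leaves open whether outcome data had been seen. It does not show that they had, or that any result was selected.
- **Every test must go into one large adjusted family.** Holm over the remaining 11 × 3 − 1 = 32 tests would start at 0.05/32 = 0.0016, and few would survive. That is one possible choice, not a requirement. Treating the rest as exploratory also removes the ambiguity.

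**Conclusion.** The concern holds. As written, the plan lets any p<0.05 among at least 11 outcomes and three arms be presented as evidence that PNF or mobilization is effective, because no primary outcome, time point or contrast is named and no multiplicity control is described. This is certain from the text and is more than missing detail, since following the plan exactly can yield a false claim of effectiveness.

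The size is illustrative. Under the assumptions listed in the working, the chance of at least one false significant result is about 14% at correlation 0.9 and about 38% at 0.3 (14% to 36% with 10 per arm), against the nominal 5% for a single test. It is not a bound: unconditional pairwise tests, a second time point or more outcomes would raise it, and correlations above 0.9 would lower it.

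**What to change.** **If outcome data are unseen, or the choice is made blind to them.** Name in the SAP one primary outcome, one time point and one primary contrast, tested at two-sided 0.05. The choice is the sponsor's, since the Protocol ranks nothing. An example is the DASH disability/symptom score at the end of the 4-week treatment, PNF versus mobilization as in the title.

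If all three arms are to be primary, use a Kruskal-Wallis test on the primary outcome at 0.05, followed only if significant by the three pairwise Mann-Whitney tests. If one arm truly differs, only one true null contrast remains, so the error on that outcome stays at about 5%.

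Report every other outcome, time point and contrast as exploratory, with estimates and confidence intervals and no significance claims. If further confirmatory claims are wanted, list those tests and apply Holm to them after a significant primary result. In the three-arm version, include the three primary pairwise tests in that Holm list if strict control is needed. In a check with one arm differing by an assumed 1.5 SD on the primary outcome only, leaving them out, with all other outcomes in the list, gave a familywise error of 5.4% to 7.7%; including them gave 1.1% to 3.1%.

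**If outcome data have been seen.** No confirmatory primary can be created. Label any choice as post hoc, and either adjust across all tests (Holm over 33 pairwise tests at one time point starts at 0.05/33 = 0.0015, and lower if more outcomes or time points are analysed) or report all outcomes as exploratory.

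**Cost.** A few sentences in the SAP, and no extra patients or visits. The other outcomes lose confirmatory status. If the data have been seen the cost is larger, because a prespecified confirmatory claim cannot be restored.

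### The SAP's group comparisons use rank tests without a covariate and do not say whether follow-up or change scores are tested; if pre-treatment scores exist, an adjusted analysis is usually more precise

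*Combined protocol and SAP*

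**What the plan says.** The SAP is a single paragraph. It names the software, a 0.05 significance level, a normality check ("Shapiro-Wilks test was used to investigate the appropriateness of the variables to normal distribution") and the between-group methods: "Kruskal-Wallis and Mann-Whitney U tests were used to compare the groups". It names no covariate, adjusted model, effect estimate or confidence interval. It does not say which score is ranked, and no choice of method is made to depend on the normality check.

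The protocol does not fill these gaps. The section on randomization says that participants "were randomized with 'Research Randomizer' program and divided into three groups". The section on applied evaluations describes VAS pain, DASH, Constant-Murley, range of motion and muscle strength, but not when they were measured. The treatment section gives 4 weeks of treatment and 12 of follow-up, 16 in total, without an assessment schedule.

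Two phrases could be mistaken for timing information. The pain section says "The pain severity was asked in three occasions as: at resting (VASr), during activity (VASa) and during night (VASn"; these are conditions under which pain is rated, not visits. Strength was "determined by using Baseline Push-Pull (New York, USA) dynamometer", where the word Baseline is the product name.

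**The concern.** Two things are left open.

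- **The variable tested.** If both pre-treatment and follow-up scores exist, the SAP sentence allows two different analyses, whose power can differ considerably. An analyst could choose between them after seeing the results.
- **The use of pre-treatment information.** Ranking follow-up scores ignores it. Ranking changes uses it with a fixed weight of 1, which is in general not the best weight. An adjusted analysis estimates the weight from the data.

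The contrast in the title is between two active additions to the same conventional programme: "Comparison of the Effectiveness of Proprioceptive Neuromuscular Facilitation Exercises and Shoulder Mobilization Patients with Subacromial Impingement Syndrome". The difference between them may be small, so precision matters.

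**Working it through.** **Inputs.** From the documents: three arms, the two rank tests and the 0.05 level (taken as two-sided). The documents give no sample size, SD, effect or correlation, so there is no planned figure to reproduce and every numerical input below is an assumption.

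**1. Variance with equal SDs.** Let ρ be the correlation between pre-treatment and follow-up score, and set both SDs to 1. Up to a common factor, the variance of a between-group difference is 1 for follow-up scores, 2(1 − ρ) for changes and 1 − ρ² for ANCOVA. Relative to ANCOVA this is 1/(1 − ρ²) for follow-up scores and 2(1 − ρ)/(1 − ρ²) = 2/(1 + ρ) for changes. The equivalent share of patients lost is 1 − 1/ratio.

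| ρ | Follow-up ratio (share lost) | Change ratio (share lost) |
|---|---|---|
| 0.3 | 1/0.91 = 1.10 (9%) | 2/1.3 = 1.54 (35%) |
| 0.5 | 1/0.75 = 1.33 (25%) | 2/1.5 = 1.33 (25%) |
| 0.7 | 1/0.51 = 1.96 (49%) | 2/1.7 = 1.18 (15%) |

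These ratios are for roughly normal scores and ignore the small degrees-of-freedom cost of the covariate.

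**2. Unequal SDs.** Let k = SD(baseline)/SD(follow-up). The optimal weight on the pre-treatment score is ρ × SD(follow-up)/SD(baseline) = ρ/k, and the change-score ratio becomes (1 + k² − 2ρk)/(1 − ρ²). With k = 0.7 and ρ = 0.85 the weight is 0.85/0.7 = 1.21, so a change score then gives the baseline too little weight. The change-score ratios at ρ = 0.3/0.5/0.7/0.85 are:

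- k = 0.7: 1.18/1.05/1.00/1.08
- k = 1.3: 2.10/1.85/1.71/1.73

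The follow-up ratio does not depend on k.

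**3. Power for one pair of arms.** Simulation with 20 per arm, a 0.4 SD difference and normal data:

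| ρ | Mann-Whitney, follow-up | Mann-Whitney, change | ANCOVA | Gain over the better rank test |
|---|---|---|---|---|
| 0.3 | 21% | 17% | 25% | 25 − 21 = 4 points |
| 0.5 | 21% | 22% | 29% | 29 − 22 = 7 points |
| 0.7 | 23% | 33% | 40% | 40 − 33 = 7 points |

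Allowing for simulation error and extending to ρ = 0.85, the gain is about 3 to 8 points.

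**4. Dependence on the distribution.** Three arms of 20, means 0/0.4/0.8 SD, lognormal data, ρ = 0.3/0.5/0.7 on the log scale:

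- Kruskal-Wallis on follow-up: 94/94/94%
- Kruskal-Wallis on change: 73/84/96%
- Linear ANCOVA: 67/73/84%
- Quade rank ANCOVA: 96/98/100%

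Under strong skew, linear ANCOVA loses to the better unadjusted rank test, while the rank-based adjustment does not.

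**5. Where the adjusted rank test falls behind.** Two arms of 20, 0.5 SD, heavy-tailed data (t with 3 degrees of freedom), ρ = 0.80/0.85/0.90: Quade 87.3/92.6/97.2% against Mann-Whitney on change 88.8/95.1/99.0%, a shortfall of 1.5/2.5/1.8 points.

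**6. Validity.** With no true difference, rejection rates in the main simulation stayed between 3.7% and 5.5% in all 75 settings.

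**The case against.** The strongest reply is that rank tests are a defensible choice for bounded scores such as a 10 cm VAS or a 0–100 scale, and that preferring an adjusted test is partly taste. The first half stands. A reader might infer that the planned tests are biased or invalid. The documents do not support that: patients were randomized and the tests keep their error rate.

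A second reply is that the argument about precision lacks a documented premise, because no pre-treatment measurement is described. This also stands as a limit. A reader might infer from the occasions in the pain section, or from the word Baseline in the strength section, that one was taken; neither shows it. The precision claim is therefore conditional. The unstated analysis variable is not, because that gap is visible in the SAP itself.

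Third, omnibus power exaggerates the benefit. With three arms of 20, means 0/0.4/0.8 SD, normal data and ρ = 0.5, power rises from 56% with either unadjusted test to 71% with ANCOVA, which suggests a 15-point gain. Much of that comes from the 0.8 SD gap between the extreme arms. For a single pair, which is what the title concerns, the gain is about half that or less.

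Finally, linear ANCOVA is not better for every outcome. It is the weaker choice under strong skew, and even Quade can trail slightly when ρ is high. This limits which adjusted method is chosen, but does not remove the case for adjusting.

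**Conclusion.** The point holds as a conditional matter of efficiency and pre-specification. The SAP leaves the tested variable undefined and names no method that can adjust for a pre-treatment score. If such a score exists, the planned comparison of PNF with mobilization usually yields less information than the data allow.

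For one pair of arms the gain is about 3 to 8 power points over the better unadjusted rank test, assuming 20 per arm, 0.4 SD, normal data and ρ from 0.3 to 0.85. The variance ratios for change scores also assume equal SDs before and after treatment. The true size cannot be known from the documents. The loss from using follow-up scores is small when ρ is low.

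The change is worth making because it is cheap. It does not call the validity of any result into question.

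**What to change.** - State when each outcome was assessed, including whether there was a pre-treatment assessment.
- For each outcome and assessment time, make the main between-group analysis a comparison adjusted for the pre-treatment value of the same score.
- Fix the method for each outcome in advance. Use ANCOVA with group and pre-treatment score, reporting the adjusted PNF-versus-mobilization difference with its 95% confidence interval. For outcomes expected to be clearly skewed or heavy-tailed, use Quade rank ANCOVA.
- Keep the Kruskal-Wallis and Mann-Whitney tests as sensitivity analyses on one named variable, either follow-up score or change.

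**Cost.** SAP wording and slightly more analysis work, with no new data if pre-treatment scores were recorded. Quade gives a test but no difference on the score scale. At ρ of about 0.80 and above with heavy-tailed data, it can fall a few points below the change-score rank test.

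**Limits.** The SAP is written in the past tense. If the data have already been analysed, the adjusted analysis must be labelled post hoc. If no pre-treatment score was recorded, adjustment is impossible; the SAP should then say so and state that follow-up scores are tested.
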